# 6.3 Discontinuation of vaccination or study procedures

The Sponsor may terminate the trial for safety, administrative, or other reasons. Documentation explaining premature termination of the study will be forwarded to the study site, regulatory authorities, and IECs/IRBs. A complete final examination will be carried out on the participants if the study is terminated.

The Sponsor reserves the right to terminate or curtail this clinical study for any reason, including but not limited to the following:

- Risk to participant safety
- The scientific question is no longer relevant, or the objectives will not be met (e.g., slow accrual)
- Failure to comply with GCP or terms of Clinical Trial Agreement
- Risks that cannot be adequately quantified
- Ethical concerns raised by the local community or local medical care/health care authorities
- Failure to remedy deficiencies identified through site monitoring (e.g., data recording is inaccurate and/or incomplete on a chronic basis or failure to meet other identified Sponsor performance standards)
- It becomes apparent that participant enrolment is unsatisfactory with respect to quality and/or quantity

In addition, the PATH DSMB may recommend the Sponsor terminate the study based on review of safety data or interim analysis. If the study is prematurely discontinued by the Sponsor for any reason, a summary report will be submitted to regulatory authorities. The summary report will

provide a brief description of the study, the number of participants exposed to the vaccine, dose and duration of exposure, details of adverse drug reactions, if any, and the reason for discontinuation of the study.

# 6.4 Participant Discontinuation/Withdrawal from the Study

Participation in the study is strictly voluntary. Participants have the right to decline study treatment or procedures for any reason and at any time during the study. If a participant declines further vaccination or study procedures this will be recorded as a study deviation and the reason will be clearly documented in the source document. The participant will be encouraged to complete the remaining applicable safety related follow-ups and immunogenicity blood draw. If the participant does not wish to remain in the study by declining any follow-ups or procedures, the participant can choose to withdraw consent and be withdrawn from the study as per section 6.5

Discontinuation from further vaccination may be at the discretion of the Principal Investigator if it is in the interest of the subject or based on the DSMB safety review as per section 9.2. In addition, participants will be discontinued from further vaccination for the following reasons:

- Pregnancy
- Ineligibility (either arising during the trial or retrospectively having been overlooked at screening)
- Significant protocol deviation
- Significant non-compliance with treatment regimen or trial requirements
- An adverse event that requires discontinuation of study treatment or results in inability to continue to comply with trial procedures
- Intercurrent illness or diseases or medical treatment that occur during the trial and might influence the study results or ability to continue to comply with trial procedures

The reason for withdrawal will be documented in source document and relevant CRF.

In the event of withdrawal from study, reasonable efforts should be made to conduct the following procedures:

- Review memory aid if still in use prior to withdrawal
- Updating any ongoing AE/SAEs that remain ongoing at time of subject's last visit prior to withdrawal
- Query about AEs, SAEs and concomitant medications if the interval between the subject's last visit and the time of withdrawal is within the protocol defined reporting period
- Physical examination
- Blood for immunologic testing, if applicable
- Update contact information of the study participants

## 6.5 Lost to follow-up

To avoid participants being lost to follow-up, participants will be reminded of their clinic visit by phone call, text message, or home visit 3 days or within a period deemed appropriate by site staff before scheduled visits. In the event of a missed visit, participants will be contacted by phone, or text message the next business day following the missed visit. In case the participant cannot be reached by phone, a home visit will be done to remind the participant of study visit. A participant

who cannot be located after 3 contacts and has missed 2 consecutive visits may be considered lost to follow-up. Efforts to contact the participant will be documented in source documents. Any participant who fails to attend the final study visit will also be classified as lost to follow-up. There will be no replacement of participants who are lost to follow-up.

## 6.6 Use of concomitant vaccine(s) during the study

HPV vaccine mass immunization campaign in the targeted countries are currently not planned and GAVI-supported demonstration projects have been discontinued in both the countries on HPV vaccines.

Routine vaccinations, which are listed in the exclusion criteria (section 4.3) should not be given 4 weeks prior and after each dose of study vaccination. However, administration of rabies, tetanus, COVID-19 or other types of vaccine for prevention or post-exposure indications will take priority over the study considerations. Such vaccines used during the study will be reported in the Concomitant Medication CRF.

# 6.7 Management of pregnancy during study

If a female participant becomes pregnant following vaccination, she will be encouraged to complete remaining visits and safety follow up but will not receive any further vaccination. The investigator is required to notify the CRO within 24 hours of confirmation of a pregnancy.

All efforts will be made to continue to follow any participant who becomes pregnant during the period between vaccination and the last study visit, for pregnancy outcome, even if birth occurs after the scheduled end of the study for the subject. The pregnancy and its outcome will be reported on the Pregnancy CRF. Participants who become pregnant after vaccination will be followed to term. Following birth, investigators will arrange to refer the mother and the child to a local pediatrician and/or obstetrician for consultation and this consultation report will be submitted to the IRBs. The following information will be gathered for outcome: date of delivery; health status of the mother and child, including the child's gender, height, and weight. Complications and/or abnormalities should be reported, including any premature terminations. A pregnancy is reported as an AE or SAE only when there is suspicion that the vaccine may have interfered with the effectiveness of contraception or there was a serious complication in the pregnancy, including a spontaneous abortion or an elective termination for medical rationale.

# 6.8 Clinical procedures

# Vital Signs

- Temperature in degrees Celsius (recorded to the nearest 0.1 degree) will be measured by oral or axillary thermometer.
- Respiratory rate in breaths per minute.
- Heart rate in beats per minute will be measured by automated device or manually.
- Systolic and diastolic blood pressure will be obtained and measured in millimeters of mercury by automated device or manually.

#### Height and Weight

- Height is measured and recorded to the nearest cm.
- Weight is measured in kg and recorded to the nearest 0.1 kg.

#### Physical Examination

Full physical examination (at screening and before each vaccination) will include assessment of vital signs, head, eyes, ears, nose, oropharynx, neck, chest (auscultation), lymph nodes (neck, supraclavicular, axillary, inguinal), abdomen (auscultation and palpation), musculoskeletal, skin (especially injection sites), and neurological.

#### Targeted physical examination

A focused physical examination based on symptoms reported by the participant and the presence or absence of solicited adverse events collected to assess local and systemic vaccine reactogenicity or intercurrent events.

#### Medical History

A comprehensive medical history will be collected including details of any previous vaccinations and reaction to vaccinations, participation in clinical trials, surgery, previous hospitalization, allergy to food/drugs, current medication, and history of any chronic or recurrent medical conditions.

An interval medical history will consist of inquiring regarding changes since the last medical history discussion (healthcare events, signs, symptoms, and changes in use of prescription or nonprescription drugs or herbal preparations).

# **Injection Site Examination**

Injection site assessment will be done by trained study personnel. Timing and severity grading of local reactions will be according to section 8 (safety assessment) and toxicity grading scale in Appendix II respectively.

The following parameters for reactogenicity will be assessed during the 7 days after each study vaccine injection.

- Local reactogenicity
  - o Pain
  - Swelling
  - Erythema (redness)
  - Induration
  - Pruritus
  - Abscess
- Systemic reactogenicity
  - Fever (oral or axillary temperature ≥ 38.0°C),
  - Headache
  - Vomiting
  - Nausea
  - o Fatigue
  - Chills
  - Muscle Pain
  - Cough

- Diarrhea
- Dizziness
- o Allergic dermatitis
- Rash
- Syncope
- o Anorexia

#### 6.9 Measures related to COVID-19

During the course of the study, any guidelines and their updates issued by local authorities related to public health crisis, such as COVID-19, will need to be complied with.

Please see Appendix III for such guidelines in Ghana.

# 7 LABORATORY EVALUATIONS / REQUIREMENTS

## 7.1 Sample collection, distribution, and storage

Serum specimens collected for assessment of immunogenicity will be separated into aliquots per study-specific process and timelines outlined in the Study Laboratory Manual and stored at ≤-20° C before being shipped to Frederick National Laboratory for Cancer Research. Samples will be stored in monitored, controlled-temperature freezers, with backup power supply to assure proper sample storage. Back-up specimens will be retained in storage at each site through the end of the study and verification of study results.

At the discretion of PATH, quality assurance audits may be conducted to ascertain adequate processing of immunogenicity specimens. Following testing, residual specimens will be stored at -80° C until long term storage at a designated biobank facility (TBD).

# 7.2 Immunological laboratory assays

The immunological assays to be performed include:

- Anti-HPV Type 16 and 18 IgG by ELISA
  - Anti-HPV Type 16 and 18 Pseudovirion-based neutralization assay (PBNA)

The details of the assay will be in the study Laboratory Manual. Since neutralization assays are labor intensive, technically more complex, and not currently amenable to high throughput, IgG by ELISA is chosen as primary endpoint determinant to demonstrate a response to the vaccine. There is good correlation established between PBNA and ELISA. Samples will be selected via stratified

random sampling using the Advantage eClinical system to achieve a representative sample (20% of subjects) by study arm and site for PBNA assessment.

Samples sent to the laboratory will include a sample ID which links samples to subjects. The laboratory personnel in charge of performing the immunological testing for all immunogenicity endpoints will not be provided with the randomization list containing the treatment allocation.

## 7.3 Assays qualification, standardization, validation

All assays employed to determine study endpoints must be properly validated; research assays should be standardized and run with adequate controls.

# 7.4 Future use of stored samples

Additional samples may be shipped for storage at other laboratories or repositories. Samples will be retained in accordance with regulatory guidance for retention of essential study documents, provided that the integrity of the stored sample permits testing. Subject or subject's parent/LAR will be informed about and asked whether they agree to the long-term storage of the subject's specimens for use in future research as part of the informed consent process. Any new research on the stored samples will require approval by appropriate ethics committees, including the ethics committees of the countries where the study is conducted. At study closure, PATH may store the consented samples that are not stored on site at a designated biobank facility (TBD) for at least 5 years.

#### 7.5 Biohazard containment

As transmission of blood-borne pathogens can occur through contact with contaminated needles, blood, and blood products, appropriate blood and secretion precautions will be employed by all personnel in the drawing of blood samples, as well as shipping and handling of all specimens for this study as recommended by the United States Centers for Disease Control and Prevention. All biological specimens will be transported using packaging mandated by United States Code of Federal Regulations (CFR) 42 Part 72. All dangerous goods materials, including diagnostic specimens and infectious substances, must be transported according to instructions detailed in the International Air Transport Association Dangerous Goods Regulations. Biohazardous waste will be contained according to institutional, transportation/carrier, and all other applicable regulations.

All protocol specimens will be shipped using packing that meets requirements specified by the International Air Transport Association Dangerous Goods Regulations for UN 3373, biological Substance, Category B, and Packing Instruction 650. Culture isolates, if obtained in this study, are to be shipped as specified for United Nation 2814 Category A Infectious Substances.

# 8 SAFETY ASSESSMENT AND REPORTING

#### 8.1 Definitions

#### 8.1.1 Adverse Event (AE)

An adverse event is any untoward medical occurrence in a participant after administration of the investigational vaccine and that does not necessarily have a causal relationship with the investigational vaccine. An AE can therefore be any unfavorable and unintended sign (including

abnormal laboratory findings), symptoms, physical examinations, or disease temporally associated with the use of the investigational vaccine, whether or not related to the investigational vaccine. This definition includes exacerbations of pre-existing conditions. Stable pre-existing conditions which do not change in nature or severity during the study are not considered AEs; however, these should be reported as part of the medical history.

**Solicited AEs** are pre-specific local and systemic adverse events that are common or known to be associated with vaccination that are actively monitored as indicators of vaccine reactogenicity. Investigators will not be required to assess causality of solicited adverse events if the onset is during the solicitation periods.

For this trial, solicited AEs will be assessed by study staff 30 minutes after each vaccination then daily for 7 days by the participants (data to be collected for Days 1 through 7). Participants will be provided a memory aid to record the presence or absence of solicited AEs, severity of the solicited AEs and use of concomitant medication.

The following specific solicited adverse events will be monitored for this trial:

Possible Solicited Adverse Events						
Local/Injection Site General/Systemic						
Pain	Fever (oral or axillary temperature ≥ 38.0°C)					
Erythema/redness	Headache					
Swelling Vomiting						
Induration	Nausea					
Pruritus	Fatigue					
Abscess	Chills					
	Muscle pain					
	Cough					
	Diarrhea					
Dizziness						
	Allergic dermatitis					
Rash						
	Syncope					
	Anorexia					

**Unsolicited AEs** are any AEs reported spontaneously by the participant, identified during interview at study visits, observed by the study personnel during study visits or those identified during review of medical records or source documents. Solicited adverse events with onset after the solicitation period and through Day 30 post-vaccination will be captured as unsolicited AEs (see below).

In the absence of a diagnosis, abnormal physical examination findings assessed by the investigator to be clinically significant will be recorded as an unsolicited AE.

## 8.1.2 Adverse drug reaction (ICH) / Suspected Adverse Reaction (FDA)

Adverse drug reaction is any AE in which the causal relationship to the investigational vaccine is at least a reasonable possibility, i.e., the relationship cannot be ruled out. Having a reasonable suspected causal relationship to the investigational vaccine qualify as adverse drug reaction. The concept of "reasonable causal relationship" is meant to convey in general that there are facts (evidence) or arguments to suggest a causal relationship.

**Suspected adverse reaction** is any adverse event for which there is a reasonable possibility that the drug (vaccine) caused the adverse event. For the purposes of IND safety reporting, "reasonable possibility" means there is evidence to suggest a causal relationship between the drug and the adverse event. Suspected adverse reaction implies a lesser degree of certainty about causality than adverse reaction, which means any adverse event caused by a drug.

**Adverse reaction** is any adverse event caused by the drug. Adverse event is a subset of suspected adverse reaction where there is reason to conclude that the drug caused the event. (FDA)

Unexpected adverse drug reaction is an adverse reaction, the nature or severity of which is not consistent with the information in the Investigator's brochure. (ICH)

Unexpected suspected adverse reaction is considered "unexpected" if it is not listed in the investigator brochure or is not listed at the specificity or severity that has been observed. (FDA)

## 8.1.3 Serious Adverse Event (SAE)

Serious adverse event is any adverse event that results in any of the following outcomes:

- Death
- 2. Is life-threatening (life-threatening means that the study participant was, in the opinion of the site PI or Sponsor, at risk of death at the time of the event; it does not refer to an event which hypothetically might have caused death if it were more severe).
- 3. Requires inpatient hospitalization or prolongation of existing hospitalization
- 4. Results in persistent or significant incapacity or substantial disruption of the ability to conduct normal life functions
- 5. Congenital abnormality or birth defect
- 6. Important medical event that may not result in one of the above outcomes but may jeopardize the health of the study participant or (and) require medical or surgical intervention to prevent one of the outcomes listed in the above definition of serious adverse event

**Suspected unexpected serious adverse reaction** (SUSAR) is any suspected adverse reaction that is both unexpected and serious.

# 8.2 Reporting Period and Parameter

Safety events are reported from the time of the first study injection through completion of the study. Specifically, solicited AEs to assess local and systemic reactogenicities will be collected at 30 minutes and then daily for 7 days after each vaccination. If a solicited AE started during the 7 days post vaccination and continues beyond the 7 days, it will continue to be reported as a solicited AE until resolution. Unsolicited AEs will be collected from Day 1 to the 30-day post vaccination visit after each vaccination. SAEs will be assessed from Day 1 through the end of the study for

each group. Any medical condition that is present at the time that the participant is screened will be considered as baseline and not reported as an AE. AEs characterized as intermittent require documentation of onset and duration of each episode.

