# 2.3.2.2 Secondary Safety Endpoints:

- Number of subjects in each study arm reporting solicited adverse events within 7 days after each dose
- Number of subjects in each study arm reporting unsolicited adverse events within one month after each dose
- Number of subjects in each study arm reporting serious adverse events (SAEs) occurring at any time throughout study participation

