### 4.2 Inclusion Criteria

- 1. A healthy (determined by investigator's assessment following medical history and physical examination) female between the ages of 9 14 years (all inclusive) at time of enrollment
- 2. Ability and willingness to provide parental consent and, if applicable based on local incountry regulations, participant assent.
- 3. Parent/LAR provides informed consent
- 4. Anticipated ability and willingness to complete all study visits and evaluations
- 5. Living within the catchment area of the study without plans to move during the conduct of the study

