#### After vaccine administration:

- Observe subject for 30 minutes for immediate reactogenicity, post vaccination check for solicited adverse event / reactogenicity per section 8.1.1
- Before discharge from the study clinic, the participant will be provided with supplies (including a thermometer for daily temperature recording and a memory aid to record solicited AE information for the next 7 days) and instructed in their use, and follow-up visit information and contact telephone numbers for study staff will be provided. Participants are to be instructed to contact study staff for any solicited AE greater than mild and for any events they perceive as serious.
- Participants will be called or visited in their homes daily through 7 days post-vaccination to verify daily completion of the memory aid.

Randomization is defined as the process of assigning a participant to a study arm; assignments are made by a DMC computer-generated by the Protocol Statistician. The first study vaccination (Day 1) must occur within 24 hours of randomization otherwise the participant is ineligible for continued study participation. Participants will be replaced if randomized but not vaccinated. The evaluations obtained prior to the first vaccination are the baseline for subsequent safety assessments.

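### Protocol 8.2 takes any condition present at screening out of AE reporting and leaves out the exception for worsening that 8.1.1 requires: a low-priority wording correction

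*Protocol*

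**What the plan says.** Protocol 8.2, which sets out what is reported and for how long, contains this rule: "Any medical condition that is present at the time that the participant is screened will be considered as baseline and not reported as an AE". The sentence is unconditional and does not refer to the definitions.

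Protocol 8.1.1, which defines an AE, is narrower about what is exempt. Of the AE definition it says: "This definition includes exacerbations of pre-existing conditions". It then limits the exemption: "Stable pre-existing conditions which do not change in nature or severity during the study are not considered AEs". Such stable conditions go into the medical history.

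The endpoint concerned is in Protocol 2.3.2.2: "Number of subjects in each study arm reporting unsolicited adverse events within one month after each dose". SAP 4.5.2 repeats the general AE definition. It has neither the sentence on exacerbations nor the screening exemption, so it does not decide between the two.

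**The concern.** Take a girl with a condition recorded at screening, such as a chronic skin or airway complaint, that flares in the month after a dose. Under 8.1.1 the flare is an AE. Under the words of 8.2 it is not reported. 8.2 is the section that tells sites what to report, so site staff may well work from it.

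If 8.2 were followed literally, the error could go only one way: fewer girls would be counted with an unsolicited AE than the protocol's own definition requires. The exemption has no time limit, so it would apply equally after a second dose given 24 months after the first (Groups 3 and 5).

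**Working it through.** **Step 1. The two rules side by side.**

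| Condition noted at screening, then after vaccination | 8.1.1 | 8.2, read literally |
|---|---|---|
| Unchanged | Not an AE | Not reported |
| Worsens, not serious | AE | Not reported |
| Worsens and meets a seriousness criterion | AE, hence SAE under 8.1.3 | Not reported as an AE |

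The rules agree on the first row and differ on the other two. The third row follows because 8.1.3 builds the SAE definition on the AE definition: whatever is not an AE cannot be an SAE.

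**Step 2. Does another sentence supply the missing exception?**

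- Protocol 6.2.2: "The evaluations obtained prior to the first vaccination are the baseline for subsequent safety assessments". This supports reading baseline as a reference for later change, but it gives no rule for worsening.
- Protocol 8.1.1: "In the absence of a diagnosis, abnormal physical examination findings assessed by the investigator to be clinically significant will be recorded as an unsolicited AE". This covers findings without a diagnosis. A flare of a condition already diagnosed at screening falls outside it.
- Protocol 8.2: "AEs characterized as intermittent require documentation of onset and duration of each episode". This applies to events already classed as AEs. It does not say whether an episode of a screened condition is one.
- Protocol 8.7.1 requires all SAEs to be reported to the CRO, but what counts as an SAE still depends on the AE definition.
- The solicited-event rules in 8.1.1 and 8.2 do not exempt solicited terms from the 8.2 screening sentence.

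None of them closes the gap.

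**Step 3. Size.** The documents give no frequency of conditions at screening, so the number of events at risk cannot be calculated. What can be shown is the effect per girl, with n = 205 per arm (Protocol 11.3) and Clopper-Pearson 95% intervals (Protocol 11.5.2.2).

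- Check of the method against the plan: with no events, the upper limit is 1 − 0.025^(1/205) = 1.78%, which agrees with the 1.8% in Protocol Table 2.
- Each girl whose only unsolicited AE is left out lowers the arm's percentage by 1/205 = 0.49 points.
- For comparison, the interval half-widths at three illustrative counts (assumed, since the documents give no expected rate) are:

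| Count | Percentage | 95% interval | Half-width |
|---|---|---|---|
| 20/205 | 9.8% | 6.06% to 14.67% | 4.3 points |
| 41/205 | 20.0% | 14.75% to 26.14% | 5.7 points |
| 62/205 | 30.2% | 24.04% to 37.03% | 6.5 points |

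At these rates one omitted girl is well inside the sampling uncertainty.

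**The case against.** The strongest reply is that this is abbreviated wording, not a true conflict. Section 8.1 holds the definitions and 8.1.1 settles what an AE is. Section 8.2 mainly deals with collection periods. If a condition at screening is the baseline, then the condition as found is not an AE, but a later departure from it is. On that reading both sections can be followed, and harm arises only if a site acts on one sentence of 8.2 and disregards a clear definition shortly before it. Nothing in the documents suggests that sites do so. Interval history is taken at follow-up visits (Protocol 6.8 and Appendix I), so a flare would probably be mentioned. Further reporting detail sits in a Safety Management Plan that is not among the documents.

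Most of this stands. 8.1.1 does state the intended rule, and the effect is speculative. What remains is that 8.2 does not say baseline for comparison; it says the condition is not reported. Hearing of a flare during history-taking does not ensure that it is entered as an AE.

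Two further inferences should be resisted. A reader might suppose that SAEs and solicited terms in the 7-day window are safe from the problem. The text does not give them separate protection: if they are safe, it is because 8.1.1 governs, and then non-serious flares are safe for the same reason. Conversely, a reader might infer that serious events will go unreported, or that the pause rule in 9.3, which one vaccine-related SAE triggers, is disabled. The documents do not support that either, given 8.1.1 and the duty in 8.7.1 to report every SAE.

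**Conclusion.** The point holds as a drafting inconsistency of low priority. Read literally, the 8.2 sentence contradicts the protocol's own AE definition, and no other sentence supplies the exception. Any resulting error would be an undercount of a secondary safety endpoint, and the same literal reading extends to serious worsening.

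The size cannot be estimated. It is likely small, because eligibility requires good health on the investigator's "assessment following medical history and physical examination" and because 8.1.1 states the intended rule plainly. The figure of 0.49 points per girl is a sensitivity, not a forecast; it assumes 205 girls in the denominator and that the omitted event was her only unsolicited AE. The primary GMC comparisons do not depend on AE reporting and are unaffected.

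**What to change.** Add to the end of the 8.2 sentence: *unless it worsens in nature, severity or frequency after vaccination, in which case it is reported as an AE (or SAE if criteria are met; see 8.1.1)*. This can go in with the next protocol amendment. Remind both sites, for all arms, at the same time.

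No new data, visits or analyses are needed, because medical history is taken at screening and updated at every later visit (Appendix I). There are two small downsides. Reported AE counts may rise slightly. And if site practice actually changes while the trial is running, ascertainment could differ slightly between arms, because the visit one month after the second dose falls at Day 210 in Groups 1 and 4, Day 395 in Group 2 and Day 760 in Groups 3 and 5. If sites already follow 8.1.1, the change only tidies the text.
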